**Table 9.10-1: Timepoints and Windows for EORTC-QLQ-C30 and EuroQoL EQ-5D Assessments**

Nominal Timepoint	Time Window
Baseline	3 days of C1D1 dosing and prior to any study procedures
Every 4 Weeks for 6 months	Every 4 weeks (within 5 days of C1D1) for 6 months
Every 6 Weeks	Every 6 weeks (within 5 days of C1D1) for remainder of study
Follow-Up 1	If assessment is post last dose and within 76 days of last dose (if date of discontinuation is within 35 day after last dose) If assessment is post last dose and within 40 days of date of discontinuation (if date of discontinuation is greater than 35 days after last dose) If assessment is post 76 days of last dose (if date of discontinuation is within 35 day after last dose)
Follow-Up 2	If assessment is post 40 days of date of discontinuation (if date of discontinuation is greater than 35 days after last dose)

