**Table 2-2: On-Treatment Assessment CA209870**

Procedure	Cycle 1 Day 1 (Q2 weeks)	Subsequent cycles (Q2 weeks)	Notes
Outcome Research Assessment			
LCSS and EQ-5D questionnaires	X	X	For C1D1, PRO must be performed prior to first dose (day -3 to 1) Assessments will be performed every 4 weeks on day 1 ( $\pm 5$ days) for the first 6 months on study, then every 6 weeks for the remainder of the study. At study visits, PRO assessments should be assessed prior to any study related procedures and treatment. See Table 9.10-1
Clinical Drug Supplies and Study Drug Administration			
Nivolumab 240 mg Q2 weeks	X	X	Within 3 days from vial allocation, the participant must receive the first dose of study medication. Participants may be dosed no less than 12 days between doses and within 3 days from the scheduled dose Nivolumab treatment until disease progression, discontinuation due to unacceptable toxicity, withdrawal of consent, or study closure.
IRT/Clinical Drug Supplies			
Contact IRT	X	X	Dosing must be performed within 3 days of study drug vial assignment

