**Table 2-3: Follow-up Assessments CA209870**

Procedure	Follow-up Visits X01 (Day 35) ( $\pm$ 7 Days) and X02 (Day 100) a ( $\pm$ 7 Days) after Last Dose	Survival Follow-up Visits b Every 12 Weeks	Notes
Safety Assessments			
Targeted Physical Examination	X		
Targeted examination must include the cardiovascular, gastrointestinal, and pulmonary body systems and examination to specific malignancy
 
To assess for potential late emergent study drug related findings.

Adverse Events assessment	X		All AEs and SAEs must be collected up to 100 days after study drug discontinuation. SAEs that relate to any later protocol specified procedure must be collected.
Any subsequent cancer treatment information	X	X	
Vital signs	X		28 days from the date of last study treatment
Laboratory Tests			
Hematology and chemistry	X		
Laboratory assessments will be performed locally.
 
See Section 9.4.3

Thyroid function testing	X		TSH with free T3 and free T4
Pregnancy test	X		WOCBP only: serum or urine
Outcome Research Assessment			
LCSS and EQ-5D questionnaire	X	X	
Both LCSS and EQ-5D will occur in FU Visits 1 & 2.
 
During Survival Visits, the EQ-5D will be collected every 3 months (<math>\pm</math> 14 days) for the first year of Survival Phase, then every 6 months thereafter.
 
May be obtained through a telephone call or clinic visit.
 
See Table 9.10-1

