**Table 2-3: Follow-up Assessments CA209870**

Procedure	Follow-up Visits X01 (Day 35) ( $\pm$ 7 Days) and X02 (Day 100) a ( $\pm$ 7 Days) after Last Dose	Survival Follow-up Visits b Every 12 Weeks	Notes
Efficacy Assessments			
Radiographic tumor assessment	X	X	Only for participants without progression. Use same imaging method as was used at screening/baseline.
Participant status	X	X	Every 3 months after X02; may be accomplished by visit or phone contact, to update survival information

a Participants must be followed for at least 100 days after last dose of study treatment. Follow-up visit number one X01 (FU1) occurs approximately 35 days ( $\pm$  7 days) after the last dose or coinciding with the date of discontinuation ( $\pm$  7 days) if date of discontinuation is greater than 30 days after last dose. Follow-up visit X02 (FU2) occurs approximately 100 days ( $\pm$  7 days) from last dose.

b Survival Follow-up visits to occur every 3 months from Follow-up Visit 2. First Survival visit to occur 3 months ( $\pm$ 14 days) from Follow-up visit 2. BMS may request that survival data be collected on all treated participants outside of the protocol window. At the time of this request, each subject will be contacted to determine their survival status unless the subject has withdrawn consent for all contacts.

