#### **10.3.3.1 *Patient Reported Outcomes***

The LCSS and EQ-5D completion rates, defined as the proportion of questionnaires actually received out of the expected number will be calculated and summarized at each assessment point. The EQ-5D (with two essential components: the EQ-5D descriptive system and the EQ visual analogue scale (EQ VAS) will be used to assess the subject's overall health status. Proportion of subjects reporting problems for the 5 EQ-5D dimensions at each assessment time point will be summarized by level of problem. Percentages will be based on number of subjects assessed at assessment time point. Value set for Chinese population will be used to get utility values for each individual. The baseline and change from baseline of the EQ-5D and LCSS scores at each assessment point will be summarized using descriptive statistics. The disease-related symptom deterioration rate at week 12 and week 24 as measured by LCSS and its corresponding 95% CI will also be calculated by Clopper-Pearson method. All summaries for LCSS and EQ-5D will be done for all treated participants, and also by tumor histology (SQ or NSQ), by PD-L1 expression (PD-L1 negative or PD-L1 positive), by infection status (HBV infection or non-HBV infection), and by molecular type (EGFR mutation, ALK translocation, or WT).

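### When treatment is discontinued late, the PRO window table in Protocol Table 9.10-1 places the day-100 Follow-Up 2 form in Follow-Up 1

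*Protocol*

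**What the plan says.** The Schedule of Activities (Protocol Tables 2-2 and 2-3) sends LCSS and EQ-5D to Table 9.10-1, titled "Timepoints and Windows for EORTC-QLQ-C30 and EuroQoL EQ-5D Assessments", for timing. SAP Appendix 1 repeats the pointer but does not reproduce the table. SAP Appendix 2 gives a general method for slotting observations into planned visits, without PRO-specific bounds.

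On follow-up:

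- Table 2-3 requires both instruments at both visits: "Both LCSS and EQ-5D will occur in FU Visits 1 & 2".
- Table 2-3, footnote a, dates the second visit from the last dose: "Follow-up visit X02 (FU2) occurs approximately 100 days", with a 7-day margin either way. The first visit is at about day 35, but moves to the discontinuation date ± 7 days "if date of discontinuation is greater than 30 days after last dose".
- Table 9.10-1 assigns a form to FU1 up to day 76 after the last dose when discontinuation is within 35 days of that dose. Otherwise it assigns the form to FU1 if it is "within 40 days of date of discontinuation (if date of discontinuation is greater than 35 days after last dose". Later forms are FU2.

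On treatment, Table 9.10-1 gives "Every 4 weeks (within 5 days of C1D1) for 6 months", and the six-weekly row has the same anchor. Table 2-2 says "Assessments will be performed every 4 weeks on day 1", ± 5 days.

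Protocol Section 10.3.3.1 summarises by assessment point: "The LCSS and EQ-5D completion rates, defined as the proportion of questionnaires actually received out of the expected number". It also summarises change from baseline at each point. SAP Section 7.8.2 plans the same.

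**The concern.** The two tables measure follow-up from different origins. FU2 is scheduled from the last dose, but the boundary between FU1 and FU2 moves with the discontinuation date. If dosing is held for a long time before treatment is formally stopped, the boundary can pass the date on which FU2 is due. A form completed on time at FU2 is then analysed as FU1.

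At stake are the LCSS and EQ-5D completion rates and changes from baseline at FU1 and FU2. An affected participant can contribute two forms to FU1 and none to FU2, and neither document says which of two forms in one window to use. Long gaps arise partly from steroid tapers for drug-related toxicity, so the mislabelling may not be random with respect to quality of life.

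**Working it through.** **Inputs.** D is the number of days from last dose to discontinuation, and t the day of the form after last dose. From Table 9.10-1, the upper bound of FU1 is day 76 if D ≤ 35, and D + 40 if D > 35. From Table 2-3, FU2 is due on days 93 to 107 (100 ± 7). Also from Table 2-3, FU1 for late discontinuation is due on days D − 7 to D + 7.

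**The table's own figure.** The first value in the second branch is D = 36, which gives 36 + 40 = 76. The two branches meet, so this is the intended reading. The line about forms after day 76 appears with the FU1 row in the text available to me. I read it as belonging to FU2, and nothing below depends on it.

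**Threshold.** A form on day t is placed in FU1 when t ≤ D + 40, that is, when D ≥ t − 40:

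- t = 93: D ≥ 53
- t = 100: D ≥ 60
- t = 107: D ≥ 67

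| D | FU1 ends on day | Form on day 93 | Form on day 100 | Form on day 107 |
|---|---|---|---|---|
| 35 | 76 | FU2 | FU2 | FU2 |
| 42 | 82 | FU2 | FU2 | FU2 |
| 52 | 92 | FU2 | FU2 | FU2 |
| 53 | 93 | FU1 | FU2 | FU2 |
| 60 | 100 | FU1 | FU1 | FU2 |
| 67 | 107 | FU1 | FU1 | FU1 |
| 84 | 124 | FU1 | FU1 | FU1 |

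Up to D = 52 every on-time FU2 form is labelled correctly. From D = 67 none is. At D = 60, forms completed on days 60 and 100, both on schedule, are both labelled FU1.

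**Can D reach 53?** Protocol Section 8.1 requires discontinuation when a delay exceeds 6 weeks (42 days) from the previous dose. It excepts prolonged steroid tapers and approved non-drug-related reasons, and states no upper limit for either. SAP Section 7.4.2.1 has a delay category above 42 days, with delay defined as cycle length minus 14. The SAP therefore provides for gaps between doses of more than 42 + 14 = 56 days.

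**Effect per participant.** Each affected participant with an on-time FU2 form lowers the FU2 completion rate by 1/n, where n is the number expected at FU2. If all 400 treated participants were expected, that is 1/400 = 0.25 percentage points. In the HBV group of 60 it is 1/60 = 1.7 points. Fewer will be expected in practice, so these are minimum values.

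**A second overlap, within Table 2-3.** The moving FU1 window reaches day 93 when D + 7 ≥ 93, that is, from D = 86. At D = 100 both visits are due on days 93 to 107. From D = 86, no boundary based on days alone can separate the two visits.

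**The case against.** The strongest reply is that this is a corner case in exploratory, descriptive output. It needs at least 53 days between last dose and discontinuation. A delay just over 42 days is not enough, and the documents give no frequency. That stands, and it limits the weight of the point. It does not remove the conflict, because the gap is permitted and no SAP rule overrides Table 9.10-1.

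Several stronger readings are tempting, but the documents do not support them:

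- A reader might infer from the title that LCSS has no valid window. Table 2-2 and SAP Appendix 1 name LCSS and give day 1 ± 5 days; Table 2-3 dates the follow-up visits. EORTC otherwise appears only in the abbreviation list, so the title looks like a leftover.
- A reader might infer from the C1D1 wording that no form after the first week counts. Read literally, none of weeks 4 to 24 (days 29 to 169) qualifies. But the same cell calls for forms every 4 weeks, and Table 2-2 supplies the evident meaning.
- A reader might infer that the week 12 and week 24 deterioration rate is compromised. It counts a 10-point ASBI increase at any time from first dosing up to those weeks. It is cumulative and does not depend on the FU1/FU2 boundary.
- A reader might infer that the 30-day versus 35-day switch point misplaces forms. The tables differ only for D = 31 to 35. There Table 2-3 puts FU1 between day 24 (31 − 7) and day 42 (35 + 7), inside the day-76 limit, and FU2 at days 93 to 107 remains FU2.
- A simple remedy would call every day 93 to 107 form FU2. That fails from D = 86, when a correctly timed FU1 form can fall on day 93 or later.

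**Conclusion.** The point holds, with limited reach. For discontinuation more than 35 days after the last dose, Table 9.10-1 and Table 2-3 are incompatible once D reaches 53 to 67, depending on the day of the FU2 form; for a form on day 100 the threshold is D = 60. The result is mislabelled FU1 and FU2 forms in the by-visit LCSS and EQ-5D summaries. This assumes that Table 9.10-1 is applied as written and that the FU2 visit takes place on schedule. The number of participants affected is unknown. The primary safety endpoint, the efficacy endpoints and the deterioration rate are not touched by this boundary. The title and the C1D1 wording are drafting slips whose meaning can be recovered from Table 2-2.

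**What to change.** Replace the late-discontinuation rule in Table 9.10-1 and state the new rule in the SAP:

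- For D > 35, FU1 ends on the earlier of D + 40 and day 92 after the last dose; later forms are FU2. Up to D = 52 nothing changes (52 + 40 = 92). At D = 60 the bound becomes day 92 instead of day 100. At D = 85 the scheduled FU1 visit (days 78 to 92) still falls wholly in FU1.
- For D ≥ 86, assign the form by its collected visit label. SAP Appendix 2 already uses the collection instrument's visit code when a date is missing. Tables 2-3 and 9.10-1 must also be reconciled, because the overlap there comes from Table 2-3 itself.

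In the same edit, retitle the table for LCSS and EQ-5D, and replace the C1D1 anchor with ± 5 days of each scheduled day 1, as Table 2-2 states. Use one switch point in both tables; this is for consistency only.

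The cost is one corrected table, a short SAP paragraph and some programming before database lock. No new data are needed.

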## **10. STATISTICAL CONSIDERATIONS**

### **10.1 Sample Size Determination**

The incidence rate of treatment related select high grade AE is 0.5-3% of nivolumab 3mg/kg every two weeks with infusion time no less than 30 minutes based on the Checkmate 153 study which published in ASCO 2016, and a PPK model predicted overall nivolumab exposures

across participants with a wide range of body weight (35-160 kg) for a 240 mg every 2 weeks flat dose to be similar to that from 3 mg/kg every 2 weeks, so we assume that the incidence rate of treatment related select high grade AE is similar in both 3 mg/kg every 2 weeks and 240mg every 2 weeks.

In order to further characterize the frequency and outcome of the rather infrequent treatment related select adverse of high grade (Grade 3-5), the current study will treat approximately 400 participants (assuming 340 non-HBV infected participants and 60 HBV infected participants) with nivolumab. The 95% confidence intervals of the incidence rate of high grade (grade 3-5) treatment related select adverse events were listed as below table. With the screen failure rate of 15%, totally 470 participants will be screened.

Table 10.1-1 shows the CI using Clopper Pearson methods for a sample size of 340 non-HBV infected participants and all treated participants.

**Table 10.1-1: 95% Confidence Intervals of Adverse Event Rate**

AE Incidence Rate	Non-HBV (340 participants)	Overall (400 participants)
0.5%	0.07%, 2.11%	0.06%, 1.79%
1%	0.32%, 2.98%	0.27%, 2.54%
3%	1.63%, 5.71%	1.56%, 5.18%

## 10.2 Populations for Analyses

The following defined population will apply to pooled tumor types and individual tumor histology and molecular genotype, unless otherwise specified:

Population	Description
Enrolled participants	All participants who signed an informed consent form and were registered into the IRT.
Treated participants	All enrolled participants who received at least one dose of study drug.
All response evaluable participants	All treated participants who have baseline and at least one on-study evaluable tumor measurement.
Non-HBV infected participants	All treated participants with HBVsAg negative by serum testing.
HBV infected participants	All treated participants with HBVsAg positive by serum testing.
Biomarker participants	All treated participants with available tissue/blood samples.

## 10.3 Statistical Analyses

Statistical analyses will be performed for pooled for each histology and molecular genotype type unless otherwise specified.

Demographic and baseline laboratory results will be summarized using descriptive statistics for all treated participants. Baseline characteristics, including demographics (age, gender, geographic location, race/ethnicity) and clinical characteristics (date of diagnosis, disease stage, liver function status, performance status, co-morbidity/prognostic indicators, location of metastases) will be collected at the time of treatment initiation for each cohort. General descriptive statistics, including mean and standard deviation (SD) for continuous variables, count and percentage for categorical variables will be used extensively to examine these variables.

The statistical analysis plan will be developed and finalized before database lock, will describe all planned analyses, and procedures for accounting for missing, unused, and spurious data. A summary of planned statistical analyses of the primary and secondary endpoints is in Section 10.3.1 and [Section 10.3.2](#).

### 10.3.1 Efficacy Analyses

Endpoint Definition	Statistical Analysis Methods
Primary	
Not applicable	
Secondary	
Overall Survival (OS) is defined as the time from the first dosing date to the date of death. Participants without documentation of death will be censored on the last date the participant was known to be alive.	Time to event distribution will be estimated using Kaplan Meier techniques. Median OS along with 95% CI will be constructed based on a log-log transformed CI for the survivor function. OS Rates at fixed timepoints (6, 12, 18, and 24 months) will be derived from the Kaplan Meier estimate and corresponding confidence interval will be derived based on Greenwood formula for variance derivation and on log-log transformation applied on the survivor function.
Time to Treatment Failure (TTF) is defined as the minimum of the time from treatment assignment to disease progression (determined by investigator assessments using RECIST 1.1), death or last dose date if a subject progressed, died or discontinued from treatment for any reasons other than “maximum clinical benefit” and	Time to event distribution will be estimated using Kaplan Meier techniques. Median TTF along with 95% CI will be constructed based on a log-log transformed CI for the survivor function.  Sensitivity analysis will be conducted to censor TTF for discontinuations due to patient

Endpoint Definition	Statistical Analysis Methods
“administrative reasons by sponsor”. TTF is censored at the last dose date for subjects who continued on treatment without progression (per RECIST 1.1) or death at the time of the database lock.	preference.
Progression-Free Survival (PFS) is defined as the time from first dose date to the date of the first documented tumor progression (per RECIST 1.1) or death due to any cause. Subjects who die without a reported prior progression will be considered to have progressed on the date of their death. Subjects who did not progress or die will be censored on the date of their last evaluable tumor assessment. Subjects who did not have any on study tumor assessments and did not die will be censored on their first dose date. Subjects who started any subsequent anti-cancer therapy without a prior reported progression will be censored at the last evaluable tumor assessment prior to initiation of the subsequent anti-cancer therapy.	Time to event distribution will be estimated using Kaplan Meier techniques. Median PFS along with 95% CI will be constructed based on a log-log transformed CI for the survivor function.
Objective Response Rate (ORR) is defined as the proportion of all treated subjects whose best overall response (BOR) from baseline is either a CR or PR per RECIST 1.1 criteria. BOR is determined by the best response designation recorded between the first dose date and the date of objectively documented progression or the date of subsequent anti-cancer therapy, whichever occurs first. For subjects without documented progression or subsequent anti-cancer therapy, all available response designations will contribute to the BOR determination. For subjects who continue nivolumab beyond progression, the BOR should be determined based on response designations recorded at the time of the	ORR will be summarized by binomial response rates and their corresponding two-sided 95% exact CIs using Clopper-Pearson method.

Endpoint Definition	Statistical Analysis Methods
initial RECIST 1.1 defined progression.	
Duration of Response (DOR) is defined as the time between the date of first confirmed response to the date of the first documented tumor progression (per RECIST 1.1) or death due to any cause. Subjects who neither progress nor die will be censored on the date of their last assessment. The censoring algorithm for DOR will be the same as used for PFS definition. This endpoint will only be evaluated for participants with BOR of CR or PR.	The DOR will be summarized for all treated participants who achieve confirmed PR or CR using the Kaplan-Meier (KM) product-limit method. Median values of DOR, along with two-sided 95% CI using Brookmeyer and Crowley method, will also be calculated.

#### **10.3.1.1 Efficacy Analysis in Subgroups:**

The efficacy analyses methods for OS, TTF, PFS, ORR, and DOR will also be evaluated in different subgroups, including squamous and non-squamous subgroups, PD-L1 positive and PD-L1 negative protein expression subgroups, non-HBV infected and HBV infected subgroups, and EGFR mutation, ALK positive and WT subgroups. The analyses methods described above for OS, ORR, and PFS will be repeated for each of the subgroup.

#### **10.3.2 Safety Analyses**

Endpoint Definition	Statistical Analysis Methods
Primary and Secondary	
Safety and tolerability	
Descriptive statistics of safety will be presented using NCI CTCAE version 4. All on-study AEs and SAEs and drug-related AEs and SAEs will be tabulated using worst grade per NCI CTCAE v.4 criteria by system organ class and MedDRA preferred term.
 
On-study lab parameters including hematology, chemistry, liver function, thyroid function, and renal function will be summarized using worst grade per NCI CTCAE v.4 criteria.

#### **10.3.3 Other Analyses**

Exploratory analyses for [REDACTED] health outcomes [REDACTED] will be described in the statistical analysis plans finalized before database lock. These analyses will be presented separately from the main clinical study report.

#### **10.3.3.1 *Patient Reported Outcomes***

The LCSS and EQ-5D completion rates, defined as the proportion of questionnaires actually received out of the expected number will be calculated and summarized at each assessment point. The EQ-5D (with two essential components: the EQ-5D descriptive system and the EQ visual analogue scale (EQ VAS) will be used to assess the subject's overall health status. Proportion of subjects reporting problems for the 5 EQ-5D dimensions at each assessment time point will be summarized by level of problem. Percentages will be based on number of subjects assessed at assessment time point. Value set for Chinese population will be used to get utility values for each individual. The baseline and change from baseline of the EQ-5D and LCSS scores at each assessment point will be summarized using descriptive statistics. The disease-related symptom deterioration rate at week 12 and week 24 as measured by LCSS and its corresponding 95% CI will also be calculated by Clopper-Pearson method. All summaries for LCSS and EQ-5D will be done for all treated participants, and also by tumor histology (SQ or NSQ), by PD-L1 expression (PD-L1 negative or PD-L1 positive), by infection status (HBV infection or non-HBV infection), and by molecular type (EGFR mutation, ALK translocation, or WT).

